### 1. Abstract

There is a substantial body of work regarding the written anesthesia consent form. As a result, the written anesthesia consent form has become a standard requirement throughout the United States of America. However, there has been little examination of verbal aspects of anesthesia consent and of the value of the preoperative anesthesia discussion that should take place prior to surgery. Non-anesthesia medical studies have indicated that inadequate patient-physician communication and an inadequate patient-physician relationship will result in misunderstanding and an increased malpractice risk. Lack of understanding of the duties and responsibilities of anesthesiologists is also damaging to the professional status of the field of anesthesiology. This study will utilize patient interviews and questionnaires to examine the degree of awareness that the patients and their families possess regarding what general anesthesia is, the duties and responsibilities of the anesthesiologist, the role of the anesthesiologist within the operating room and the specifics of what they are agreeing to by signing the consent form. If it is determined that a more structured and thorough pre-anesthesia discussion will help patients and their families understand what general anesthesia is, understand the specific responsibilities of anesthesiology providers, understand the professional status of anesthesiologists, give them a better feeling of autonomy and better understand what they are agreeing to by signing the consent form, then there will be substantial ramifications to the priority and importance given to pre-anesthesia discussions nationwide. Secondary benefits include influences on anesthesia residency training and malpractice actions against anesthesiologists. Improved patient satisfaction with the anesthesia experience is another potential secondary benefit.

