#### 4. Study Procedures

- a. Study design, including the sequence and timing of study procedures (distinguish research procedures from those that are part of routine care).

Research Procedures will be integrated into the routine part of the preoperative pre-anesthesia session. .

A member of the study team will approach the anesthesiologists who will be in the control arm of the study. None of the study team members will be in a supervisory or evaluative role to the potential anesthesiologists to be approached. Patient participants will be approached and asked if they are interested in participating. Those who are interested and eligible will undergo the research informed consent process. Patients will be divided into a **control group** and an **intervention group**. Both groups will receive the above described post-operative questionnaires with the addition of selected questions regarding their prior experience with anesthesia, and their understanding of what the anesthesiologist is responsible for. During the post-operative questionnaire they will also be asked what percentage of the signed anesthesia consent they read and if they recall anything about it. The questionnaire will be completed postoperatively, over the phone or in person, no more than 3 days after the day of the procedure.

The **control group** will have their pre-op discussion performed by an anesthesiologist in a manner commensurate with their routine for preoperative discussion. These anesthesiologists are not part of the study team. These anesthesiologists will be approached by a member of the study team and asked for permission to participate and be observed; then their patients will also be approached for participation. These anesthesiologists will be audio-recorded. Remotely, a study team member will review the audio-recording and will use a check list to assess the content communicated during the preoperative discussion. The amount of time that the discussion takes will also be recorded.

The **intervention group** will have their pre-op discussion performed by one of the two study anesthesiologists who will perform their discussion with knowledge of specific material that must be addressed prior to completion of the discussion including:

1. Description of the type of anesthesia administered
2. Description of what that type of anesthesia is (eg. what is general anesthesia?)

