**7. Study Statistics**

- a. Primary outcome variable: Recall of risks, understanding of anesthetic plan
- b. Secondary outcome variables. Anxiety relief
- c. Statistical plan: Pearson's Chi-squared statistic for categorical variables and Mann-Whitney U Tests for scaled variables.
- d. Early stopping rules.  
Study may be stopped at any time if there is a medical or public health emergency.

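### The planned tests treat patients as independent although all intervention patients share two anesthesiologists and control patients are grouped by theirs, so p-values are too small if outcomes vary by anesthesiologist

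*Combined protocol and SAP*

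**What the plan says.** Section 7c is one sentence: Pearson's "Chi-squared statistic for categorical variables and Mann-Whitney U Tests for scaled variables". Section 7a names recall of risks and understanding of the anesthetic plan as the primary outcome, and 7b names anxiety relief as secondary. Section 4a says that the two groups' questionnaire results will be compared.

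The same section fixes who speaks to whom. An intervention patient "will have their pre-op discussion performed by one of the two study anesthesiologists". Control anesthesiologists are "asked for permission to participate and be observed; then their patients will also be approached for participation". Of the control anesthesiologists it adds: "These anesthesiologists are not part of the study team". Each anesthesiologist therefore belongs to one arm only. The number of control anesthesiologists is not given.

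Nothing in the documents mentions a mixed model, generalized estimating equations, a provider-level analysis, an ICC or a design effect. They also state no sample size, alpha or power. The Abstract says that if a more structured discussion is found to help, "there will be substantial ramifications to the priority and importance given to pre-anesthesia discussions nationwide".

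**The concern.** The intervention is a conversation, and the outcomes are what patients remember, understand and feel afterwards. Patients who heard the same speaker are likely to resemble one another on these measures. The protocol itself has each discussion recorded, timed and scored on a checklist, so it allows for delivery to differ.

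The standard error behind both named tests leaves this resemblance out. The omission matters most in the intervention arm, where each anesthesiologist accounts for about half the patients. An ordinary difference between two individuals and their colleagues could then reach p<0.05 with no effect of the structured content, and the Abstract would carry that result to national practice.

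Whether content can be told apart from provider is a separate question. Even if the contrast between arms is accepted as it stands, its p-value is calculated on the wrong variance.

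**Working it through.** The plan has no figure of its own to reproduce.

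**Inputs from the documents:** two intervention anesthesiologists; control patients grouped by anesthesiologist; no anesthesiologist in both arms; chi-squared and Mann-Whitney tests.

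**Assumed, because not stated:** 1:1 allocation, 50 or 100 patients per arm, 10 control anesthesiologists, two-sided 5%, true rate 50% in both arms, and ICC from 0.01 to 0.10, equal in the two arms unless noted.

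**Step 1, approximation.** With n patients and k anesthesiologists in an arm, the design effect is 1 + (n/k − 1) × ICC. D is the mean of the two arms' design effects. The actual error rate is 2 × [1 − Φ(1.96/√D)].

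Example, 50 per arm, ICC 0.05:
- Intervention: 1 + 24 × 0.05 = 2.20
- Control: 1 + 4 × 0.05 = 1.20
- D = (2.20 + 1.20)/2 = 1.70, so the error rate is 13.3%

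**Step 2, simulation.** Beta-binomial data with no true effect, uncorrected chi-squared, 20,000 runs per setting:

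| ICC | 50 per arm: formula | 50 per arm: simulated | 100 per arm: formula | 100 per arm: simulated |
|---|---|---|---|---|
| 0.01 | 6.6% | 7.5% | 8.4% | 9.4% |
| 0.02 | 8.3% | 9.5% | 11.9% | 13.1% |
| 0.05 | 13.3% | 15.2% | 21.1% | 22.6% |
| 0.10 | 20.6% | 22.7% | 32.1% | 34.3% |

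Part of the gap at low ICC is the uncorrected chi-squared itself, which gives about 5.4% to 5.8% at ICC 0 with 50 per arm.

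Mann-Whitney on a five-level score (ICC on the underlying normal scale, 4,000 runs) gives 6.3%, 12.4% and 18.7% at ICC 0.01, 0.05 and 0.10 with 50 per arm, and 7.7%, 19.5% and 30.3% with 100.

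**Step 3, sensitivity.**
- *Number of control anesthesiologists* (50 per arm, ICC 0.05, formula): 14.7% with 5, 12.6% with 20, 12.1% with one per patient. The intervention pair drives the result.
- *Small trial* (25 per arm, formula): 5.8% at ICC 0.01, 12.7% at ICC 0.10.
- *Unequal ICC* (0.01 intervention, 0.05 control): D is (1.24 + 1.20)/2 = 1.22 at 50 per arm and (1.49 + 1.45)/2 = 1.47 at 100. Simulation gives about 8% and 12%.

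**Step 4, limit on information.** The effective size of the intervention arm is n/(1 + (n/2 − 1) × ICC), which approaches 2/ICC as n grows. At ICC 0.05, 50 patients count as 50/2.20 ≈ 23, and no enrolment takes the arm past 2/0.05 = 40.

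**Step 5, a provider-level alternative.** Estimate a common between-anesthesiologist variance from the spread of provider results within arms, and refer the arm difference to a t distribution with 2 + 10 − 2 = 10 degrees of freedom (critical value 2.228). At 100 per arm:
- Equal ICC 0.01, 0.02, 0.05, 0.10: false positives 3.3%, 4.4%, 6.0%, 7.1%
- ICC 0.10 intervention, 0.01 control: about 13%
- ICC 0.01 intervention, 0.10 control: about 2%
- Power for 70% versus 50% at ICC 0.05: 39%, against an apparent 74% from chi-squared

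**The case against.** The strongest reply concerns size. A reader might infer that the trial's false-positive rate is well above 5% whatever happens. The documents do not support that: inflation depends on ICC and on patients per intervention anesthesiologist, and neither is stated. At ICC 0.01 with 25 to 50 patients per arm the formula gives only about 6% to 7%. With no variation between anesthesiologists there is no inflation from this source.

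Second, the ICC may differ between arms. Section 4a gives the intervention pair eight topics that they must cover, while controls follow their own routine. That could make the intervention pair more alike and reduce the inflation in the arm where it matters most. The reverse is also possible, since manner of delivery is not standardised. This widens the range and leaves the defect in place.

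Third, the remedy is fragile. Two intervention anesthesiologists leave one degree of freedom for checking a common variance, and the error rate reaches about 13% when they vary much more than the controls. The error rates in Step 5 belong to an ANOVA-type test on a binary outcome. They do not carry over to a random-intercept logistic or ordinal model, which was not checked.

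A reader might also infer that a corrected p-value would support the national claim. It would not. Anesthesiologists are nested in arms, so no model separates what was said from the two people who said it.

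All three objections stand as limits on size and remedy. None supplies the missing adjustment.

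**Conclusion.** Section 7c is wrong as written. It names only tests that assume independent patients, in a design where patients are grouped by anesthesiologist and one arm has two. This follows from the text alone. If outcomes vary by anesthesiologist at all, the p-values are too small.

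The amount is conditional. Over ICC 0.01 to 0.10, equal in the two arms, the chi-squared false-positive rate runs from about 8% to 23% at 50 per arm and from about 9% to 34% at 100 per arm, under the assumptions listed in the working. Lower ICC in the intervention arm brings it down. Confidence is high that the defect exists and moderate about any single figure.

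The correction should be made before enrolment, since the documents do not say that a provider code is kept. Section 8b removes identifiers at data entry, and without such a code the grouping could not be recovered later.

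**What to change.** **Analysis (7c).** Base the primary and secondary comparisons on an analysis that accounts for anesthesiologist. One option is a random-anesthesiologist, ANOVA-type test on provider-level results (proportions for categorical outcomes, means for scaled ones), with a common between-anesthesiologist variance and degrees of freedom equal to the number of anesthesiologists minus 2. Report chi-squared and Mann-Whitney as descriptive only. State the alpha and the expected number of anesthesiologists and patients per arm, so that the operating characteristics can be checked for the layout actually used.

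**Data.** Enter a coded anesthesiologist ID for every patient, and say in 8b that it survives de-identification.

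**Limits to state.** The analysis assumes equal between-provider variance in the two arms. It does not separate content from the two intervention anesthesiologists, and the conclusion is confined to those two. The Abstract's national claim should be reworded to match. Only having more anesthesiologists deliver the structured discussion would lift the limit in Step 4, and that is a design change beyond this correction.

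**Cost.** A few sentences in the plan and one coded field. Intervals become wider, and apparent power falls (about 74% to 39% in the example). The lower figure is the more realistic one for the assumed layout. The test is conservative when ICC is near zero, with an error rate of about 2%.

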**8. Risks**

- a. Medical risks, listing all procedures, their major and minor risks and expected frequency.  
There are no anticipated medical risks associated with participation in this study.
- b. Steps taken to minimize the risks.  
Maintain confidentiality and privacy. Give patients option to withdraw from study at any time. Wearing of masks throughout the perioperative period. Patient data will be de-identified with the Safe Harbor Method that removes 18 Protected Health Information (PHI) Identifiers. This de-identification process will be pursued at the time of data entry.
- c. Plan for reporting unanticipated problems or study deviations.  
Any unanticipated problems or deviations may be reported to the IRB.
- d. Legal risks such as the risks that would be associated with breach of confidentiality.  
There are no anticipated legal risks, including those associated with a breach of confidentiality. Participants will be de-identified during and after the data collection process.
- e. Financial risks to the participants.  
There are no anticipated financial risks to participants.

**9. Benefits**

- a. Description of the probable benefits for the participant and for society.

Participants will contribute to general knowledge in this area, and results may be shared in publications.

**10. Payment and Remuneration**

- a. Detail compensation for participants including possible total compensation, proposed bonus, and any proposed reductions or penalties for not completing the protocol.

Patients will not be compensated in this study.

**11. Costs**

- a. Detail costs of study procedure(s) or drug (s) or substance(s) to participants and identify who will pay for them.

There are no anticipated costs to patients.
